## **9. STATISTICAL CONSIDERATIONS**

### **9.1 General Design Issues**

Our analytic aim is to obtain information to estimate group means, variability, and confidence intervals, identify primary and secondary outcomes, and conduct an a priori power calculation for sample size estimation for a future fully-powered efficacy RCT. Our study aims to optimize measurement by empirically assessing the sensitivity and responsiveness of conceptually well-justified candidate measures for the future trial. Since this is not an efficacy study, no primary or secondary hypotheses have been proposed to test the impact of MBRT on outcomes; however, results from this study will be used to determine primary and secondary outcome categories for the future trial.

All of the self-report measures in this study have been validated and found to be reliable in past research. The physiological measures in this study have been validated and found to be reliable methods of assessing relevant biomarkers in past research. The behavioral measure that will be used in this study is a standardized tracking system that integrates officer, administrator, and citizen data and is considered the current “gold standard” for assessing LEO use of force. An important objective of this study is to demonstrate the potential utility of this behavioral measure as a research outcome. Preliminary review of these data suggest there is sufficient variability in departments at all study sites; however, to our knowledge, the sensitivity to between-group differences and responsiveness to changes during an intervention have not yet been assessed.

Our design is an individually-randomized group treatment trial with three arms (MBRT, SME, and NIC). This design was chosen in order to assess the sensitivity of outcome measures to between-group differences at the end of MBRT and responsiveness to changes in individual LEOs during the course of MBRT. Inclusion of three arms will document the willingness of LEOs to accept randomization to these treatment options, and enable our study staff to assess and optimize the implementation of all study procedures across a no-treatment control group, an active control group, and a treatment group at multiple study sites. This information will allow us to identify primary and secondary outcomes as well as detect and correct any procedural flaws in order to optimize procedures for a future fully-powered, multi-centered efficacy RCT.

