## **Sample Size and Population**

We will recruit 104 law enforcement officers (52 at Albuquerque, 26 at Portland, and 26 at Madison). Using a 2:1.5:1 randomization allocation ratio for MBRT, SME, and NIC conditions, respectively, across three sites, 47 participants will be randomized to MBRT; 35 to SME; and 22 to NIC. Participants will be stratified by gender to ensure equivalent gender representation across conditions.

All participants will be invited to participate in individual feedback interviews via phone after the post-course assessment.

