#### **Objective 4: Assess participant experience and optimize outcome measures across sites.**

Well-developed content themes with data saturation emerging from feedback interviews will provide information on acceptability, impact of assessments, protocol and intervention fidelity, and equivalence of these markers across sites. Benchmark sensitivity and responsiveness values will determine the most sensitive and responsive measures relative to all study outcomes, versus a significance testing approach in which standardized/conventional threshold values are used to make decisions regarding significance. Sensitivity and responsiveness information will determine which outcomes are most impacted by MBRT for retention in a future full-scale multi-site efficacy trial. Benchmarks for equivalence across sites will be evidenced by: a) qualitative themes that suggest experiential continuity across sites, and b) equivalence in outcome measure response distributions, reliability estimates, and intraclass correlations.

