## 9.2 Sample Size and Randomization

Our sample size estimate is derived from a recent conceptual framework and systematic analysis for conducting a feasibility trial in preparation for a future fully-powered efficacy RCT, as well as best practices and suggestions for extending CONSORT guidelines to feasibility trials. Sample sizes of 12-25 participants per arm are recommended to optimize estimation of group means and variability without oversampling in terms of diminishing returns in parameter estimation, and to provide reasonably precise information in terms of confidence intervals around retention rates. This range is consistent with the median treatment arm size of 18 found in a systematic review of feasibility trials, and is sufficient to assess our primary goals of optimizing study procedures and obtaining data for parameter estimation, measure sensitivity, and measure responsiveness. Given the optimization aim of our study, we did not conduct an a priori power analysis based on effect sizes and a variance inflation factor to estimate the needed sample size. Our study will provide estimates of means and variability (including intraclass correlations) that we will use for an a priori power calculation for sample size estimation in a future fully-powered efficacy RCT. Consistent with guidelines on the NIH Research Methods Resources Webpage, the proposal for the future fully-powered efficacy RCT will include a sensitivity analysis that reflects the impact of potential differences between the estimate and realized value of the intraclass correlation, the number of clusters per arm, and size and variability of those clusters, based on the data we obtain in this study.

Measure sensitivity to our study arms will be assessed by examining relative efficiency; more specifically, by dividing the *F*-value for each behavioral, physiological, and self-report outcome by the largest *F*-value among the outcomes. To generate the *F*-values for relative efficiency comparisons, we will conduct a one-way between-subjects Analysis of Variance for each outcome for MBRT vs. SME and MBRT vs. NIC. To adjust for non-ignorable clustering in order

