to obtain more accurate (i.e., unbiased)  $F$ -values, we will include study site and gender, as covariates in all ANOVA analyses (i.e., perform a one-way between-subjects Analysis of Covariance for each outcome). Assessing relative efficiency entails generating  $F$ -values for comparison purposes and does not require determining whether the group differences are significant; however, adjusting for non-ignorable clustering will allow us to avoid deviation from a type I error rate of .05 and calculate  $F$ -values that most precisely reflect group differences for each outcome. Responsiveness to change will be assessed, in part, by comparing standardized mean responses, which will not require conducting an inferential test and therefore will not be impacted by type I or type II error rates. To assess responsiveness to change, we will also calculate partial correlations with a global impression of change measure and residualized change scores for each self-reported outcome, adjusting for variability due to gender and study site. Just as for our relative efficiency assessment, examination of partial correlations will not entail significance testing, but instead generating correlation coefficients for comparative purposes; however, we will partial out variability due to gender and study site to obtain precise (i.e., unbiased) estimates of covariance between a global impression of change measure and self-report outcomes.

Based on our recent R21 study (R21AT008854), in which we had an overall attrition rate of 20% across all study arms, we predict an overall attrition rate of 20% across our three study arms.

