## **9.6 Data Analyses**

### Quantitative:

Following best practice guidelines including CONSORT feasibility guidelines and past research, we will measure sensitivity (using a relative efficiency approach) and

responsiveness to change (examining within-group change over time). Relative efficiency analyses will be used to establish that our outcome measures are sensitive to differences between our treatment arm of focus (MBRT) and our other two arms - an active control arm (SME) and a no-treatment control arm (NIC). Therefore, sensitivity analyses will focus on assessing the degree to which outcomes are sensitive to study arms and not whether change is significant. Sensitivity to differences for MBRT compared to SME and NIC will be assessed by examining the relative efficiency of each outcome variable for MBRT versus SME and NIC separately. We will calculate the relative efficiency for MBRT versus SME by conducting one-way, between-subjects Analysis of Covariance (ANCOVA) analyses with MBRT versus SME as the independent variable and each outcome variable at post-training as the dependent variable; we will include study site and gender as covariates. We will also conduct ANOVAs using the same independent and dependent variables to ensure that all inferential tests are conducted and identify any potential Type II Errors among the ANCOVAs. We will then divide the *F*-statistic for each behavioral (BlueTeam/departmental use of force; individual indicators of use of force as well as a composite score of use of force using the individual indicators), physiological (C-RP, IL-6, IL-10, TNF- $\alpha$ ), and self-report (aggression, alcohol misuse, depression, suicidal ideation, trauma symptoms, burnout, and psychological resilience) outcome by the largest *F*-statistic among these analyses, such that the larger the number, the more sensitive that outcome is to the impact of MBRT relative to the active control group.

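### Outcomes for the efficacy trial are selected by observed effect, and means from the same officers feed its power calculation, with no stated protection against an inflated target effect size

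*Combined protocol and SAP*

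**What the plan says.** Three statements have to be read together.

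- **Selection.** Section 1.1, Objective 4: "Sensitivity and responsiveness information will determine which outcomes are most impacted by MBRT for retention in a future full-scale multi-site efficacy trial". Section 9.6 ranks outcomes by F divided by the largest F, separately for MBRT v SME and MBRT v NIC, "such that the larger the number, the more sensitive that outcome is to the impact of MBRT relative to the active control group". Within the MBRT arm it also ranks by the absolute standardized mean response and the absolute correlation with global impression of change. Objective 4 sets aside conventional significance thresholds.
- **Reuse.** Section 9.1 gives the aim as to "identify primary and secondary outcomes, and conduct an a priori power calculation for sample size estimation for a future fully-powered efficacy RCT". Section 9.2 adds: "Our study will provide estimates of means and variability (including intraclass correlations) that we will use for an a priori power calculation".
- **Safeguards.** Section 9.2 promises that the efficacy proposal will carry a sensitivity analysis on the intraclass correlation and on the number, size and variability of clusters. Effect size is not among the quantities varied. Section 9.1 plans confidence intervals but gives them no role in the power calculation.

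For this trial itself, "we did not conduct an a priori power analysis based on effect sizes and a variance inflation factor". The size rests on a rule of thumb: "Sample sizes of 12-25 participants per arm are recommended to optimize estimation of group means and variability".

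**The concern.** The largest of several noisy estimates overstates its own true value, because selection favours outcomes whose chance error happened to be large. Means enter a two-arm power calculation through their difference. If the difference on an outcome that ranked high here is put into the efficacy trial's calculation, the target is too large and the sample size too small. F and absolute values also ignore direction, so an outcome that worsened under MBRT can rank high.

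At stake is one of the main products of this feasibility trial, the sizing of the efficacy RCT. No inference in the present trial depends on it.

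**Working it through.** **1. The plan's own figures.** The documents give no effect size, power or N for the efficacy trial, so the only size figure to reproduce is the split of 104 by 2:1.5:1.

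- 104 × 2/4.5 = 46.2, 104 × 1.5/4.5 = 34.7 and 104 × 1/4.5 = 23.1.
- The plan states "47 participants will be randomized to MBRT; 35 to SME; and 22 to NIC", within two participants in each arm.
- Section 9.2: "we predict an overall attrition rate of 20% across our three study arms". Applied equally to each arm (an assumption), this leaves 47 × 0.8 = 37.6, 35 × 0.8 = 28 and 22 × 0.8 = 17.6, or about 38, 28 and 18.

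**2. Noise in one observed effect.** In SD units, SE(d) ≈ √(1/n₁ + 1/n₂).

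- MBRT v SME: √(1/38 + 1/28) = 0.25.
- MBRT v NIC: √(1/38 + 1/18) = 0.29.

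The noise is about as large as a small-to-moderate effect.

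**3. Number of ranked outcomes.** Section 9.6 lists 7 self-report outcomes, 4 biomarkers and 1 use-of-force composite. That is 12, plus an unstated number of individual use-of-force indicators.

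**4. One case by hand.** Per-arm n for a two-sided 0.05 test with 80% power is 2(1.96 + 0.84)²/d² ≈ 15.7/d².

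- Assume a true d of 0.3 for every outcome and a between-outcome correlation of 0.5. The simulated median |d| of the top-ranked outcome (MBRT v SME) is 0.60.
- Planned n = 15.7/0.60² ≈ 44 per arm. Needed n = 15.7/0.3² ≈ 175 per arm.
- Power of 44 per arm at the true effect: 0.3 × √(44/2) = 1.41, and Φ(1.41 − 1.96) ≈ 0.29.
- Averaged over all simulated results instead of taken at the median, true power is 35%.

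**5. Simulation over a range.** Each of 40,000 runs draws 12 outcomes at 38 v 28, selects the largest |t| (the same order as F), sizes a 1:1 trial at 80% power on that observed d, and computes its power at the selected outcome's true d. The true effects, the correlation, the 80% power and the two-sided 0.05 are assumptions. Clustering is left out.

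Mean true power when all 12 outcomes share one true d:

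| True d | corr. 0 | 0.3 | 0.5 | 0.7 |
|---|---|---|---|---|
| 0.2 | 17% | 20% | 24% | 30% |
| 0.3 | 24% | 30% | 35% | 42% |
| 0.5 | 35% | 41% | 46% | 52% |

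Over this grid, MBRT v NIC (38 v 18) gives 14-50%, and MBRT v SME with no dropout gives 19-54%.

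Mean true power when true effects differ (MBRT v SME):

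| True effects | corr. 0.3 to 0.5 | corr. 0 to 0.6 |
|---|---|---|
| Spread over 0-0.5 | 38-41% | about 35-45% |
| Spread over 0.1-0.8 | 55-59% | about 51-63% |
| One at 0.8, rest 0.2 | 65-70% | about 58-73% |
| One at 1.0, rest 0.2 | 75-77% | not tabulated |

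These figures move by a point or two depending on whether the SD is treated as known or estimated.

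**6. Selection against plain imprecision.** At d = 0.3 and correlation 0.5, mean true power by number of ranked outcomes is 71% (1), 59% (2), 48% (4), 41% (7), 35% (12) and 30% (20). One pre-chosen outcome already falls 80 − 71 = 9 points short. Ranking 12 costs a further 71 − 35 = 36 points.

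**The case against.** A reader might infer that the plan, followed as written, yields an efficacy trial several times too small for whichever outcome ranks first. The documents do not support that.

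- **The decisive step is not stated.** No section says that the observed difference on the top-ranked outcome will be the target effect. Section 9.2 commits to means and variability, which is open to other readings, and the efficacy trial's target, power and N are left for later. This stands, and it makes the conclusion conditional.
- **Selection is not a single-winner rule.** There are two F rankings, a within-arm standardized response and a correlation with global change. No rule combines them, several outcomes may be retained, and section 9.1 restricts the pool to conceptually justified measures. This could weaken the bias but not remove it, since the rankings use observed size in the same officers.
- **Equal true effects are a harsh assumption.** Ranking then carries no information. If one outcome clearly dominates, the inflation is slight. This stands, and the unequal cases are tabulated for that reason.
- **Part of the shortfall is imprecision.** Correct, but at d = 0.3 with 12 outcomes it is the smaller part.
- **The target can still be chosen well in the later proposal, with no data lost.** Also correct. It lowers the urgency, but the plan gives the proposal no instruction to do so.

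Clustering works the other way. Section 9.6 will not adjust for intraclass correlation. With the MBRT groups of 10 to 13 in section 5.1, an assumed intraclass correlation of 0.05 inflates the variance of that arm's mean by 1 + 9 × 0.05 = 1.45 to 1 + 12 × 0.05 = 1.60, which adds noise to the rankings.

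**Conclusion.** The concern holds in conditional form. The documents select by observed effect, reuse means from the same officers for power, and name no protection on the effect size. If a selected observed difference becomes the target, its bias is upward and the efficacy trial will be underpowered.

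The documents do not fix how far. With 12 outcomes, 38 v 28 completers and correlations of 0 to 0.6, mean true power against a nominal 80% runs from about 17-50% (common true d of 0.2-0.5) to about 58-73% (one outcome at 0.8, the rest at 0.2). It comes close to 80% only when one outcome dominates strongly. This should be fixed, but it does not threaten the conduct or validity of the present trial.

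**What to change.** Amend sections 9.1 and 9.2, before outcome results are seen, to state that:

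1. The observed effect of an outcome selected in this trial will not be used unadjusted as the efficacy trial's target effect size.
2. The target will be a pre-stated important difference where one can be justified. Otherwise it will be a shrunken or lower-confidence-limit estimate. The alternative is needed because the documents give no important difference for any candidate outcome.
3. SD, baseline-to-post correlation, attrition and a range for the intraclass correlation will be taken from this trial.
4. Effects for all candidate outcomes will be reported with 95% confidence intervals, not only for those selected.
5. The sensitivity analysis promised in section 9.2 will also vary the effect size.

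The cost is wording only, with no new data. The future sample size will look less favourable.

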## 9.2 Sample Size and Randomization

Our sample size estimate is derived from a recent conceptual framework and systematic analysis for conducting a feasibility trial in preparation for a future fully-powered efficacy RCT, as well as best practices and suggestions for extending CONSORT guidelines to feasibility trials. Sample sizes of 12-25 participants per arm are recommended to optimize estimation of group means and variability without oversampling in terms of diminishing returns in parameter estimation, and to provide reasonably precise information in terms of confidence intervals around retention rates. This range is consistent with the median treatment arm size of 18 found in a systematic review of feasibility trials, and is sufficient to assess our primary goals of optimizing study procedures and obtaining data for parameter estimation, measure sensitivity, and measure responsiveness. Given the optimization aim of our study, we did not conduct an a priori power analysis based on effect sizes and a variance inflation factor to estimate the needed sample size. Our study will provide estimates of means and variability (including intraclass correlations) that we will use for an a priori power calculation for sample size estimation in a future fully-powered efficacy RCT. Consistent with guidelines on the NIH Research Methods Resources Webpage, the proposal for the future fully-powered efficacy RCT will include a sensitivity analysis that reflects the impact of potential differences between the estimate and realized value of the intraclass correlation, the number of clusters per arm, and size and variability of those clusters, based on the data we obtain in this study.

Measure sensitivity to our study arms will be assessed by examining relative efficiency; more specifically, by dividing the *F*-value for each behavioral, physiological, and self-report outcome by the largest *F*-value among the outcomes. To generate the *F*-values for relative efficiency comparisons, we will conduct a one-way between-subjects Analysis of Variance for each outcome for MBRT vs. SME and MBRT vs. NIC. To adjust for non-ignorable clustering in order

to obtain more accurate (i.e., unbiased)  $F$ -values, we will include study site and gender, as covariates in all ANOVA analyses (i.e., perform a one-way between-subjects Analysis of Covariance for each outcome). Assessing relative efficiency entails generating  $F$ -values for comparison purposes and does not require determining whether the group differences are significant; however, adjusting for non-ignorable clustering will allow us to avoid deviation from a type I error rate of .05 and calculate  $F$ -values that most precisely reflect group differences for each outcome. Responsiveness to change will be assessed, in part, by comparing standardized mean responses, which will not require conducting an inferential test and therefore will not be impacted by type I or type II error rates. To assess responsiveness to change, we will also calculate partial correlations with a global impression of change measure and residualized change scores for each self-reported outcome, adjusting for variability due to gender and study site. Just as for our relative efficiency assessment, examination of partial correlations will not entail significance testing, but instead generating correlation coefficients for comparative purposes; however, we will partial out variability due to gender and study site to obtain precise (i.e., unbiased) estimates of covariance between a global impression of change measure and self-report outcomes.

Based on our recent R21 study (R21AT008854), in which we had an overall attrition rate of 20% across all study arms, we predict an overall attrition rate of 20% across our three study arms.

When a participant drops out, we will attempt to obtain information from that LEO regarding the reason for withdrawal. This information will allow us to determine the nature of the missing data (i.e., missing completely at random, missing at random, missing not at random) for analytic purposes; assess whether the withdrawal is due to a protocol violation and if the LEO experienced an AE due to the intervention (if the LEO is in the MBRT or SME arm); and obtain information that could inform future program modifications (e.g., increase the flexibility of program delivery, reduce participant burden, etc.). All protocol violations will be handled by having the Co-PIs meet with relevant study staff to identify the nature of the violation, the reason for the violation, and potential remediations; the Co-PIs will then work with all relevant study staff to implement a remediation plan and decide on a timeframe for re-assessing the procedure to ensure the violation is not re-occurring.

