### **3. STUDY DESIGN**

The study will use an Individually-Randomized Group Treatment (IRGT) design, which will entail randomizing individuals, not groups, to an intervention that will be delivered to groups of Law Enforcement Officers (LEOs). An IRGT design is typically used when examining an intervention that is intended to be delivered to individuals or implemented at an individual level versus a Group/Cluster-randomized (GR) design that is used when the intervention is intended to be delivered and implemented at a group level. MBRT is delivered as a group, but the meditation practice is implemented at an individual level. Therefore, an IRGT design is preferable over a GR design, which is consistent with the use of an IGRT design in randomized controlled trials (RCTs) examining the efficacy of mindfulness-based interventions in the extant literature. An IRGT design will allow us to assess the impact of MBRT on individual LEOs.

The units of assignment and observation in the proposed study will be at the individual level since MBRT randomization and measurement will occur at an individual LEO level. Given that our primary objectives include assessing the sensitivity and responsiveness of all self-report, physiological, and behavioral outcomes, we will not consider any of our outcome measures to be primary or secondary measures. Our goal is to identify which outcomes are most impacted by MBRT, which will guide us in choosing primary and secondary outcomes in a future fully-powered efficacy RCT.

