Following baseline assessment, study staff not involved in data collection will randomly assign participants to a condition using SPSS and REDCap, stratifying for gender and using a permuted-block randomization procedure frequently used in mindfulness-based treatment trials to ensure balance within strata and across arms. The study statistician will create an allocation table using SPSS and upload it to REDCap, which study staff will use to implement the randomization procedure. Participants will be randomly assigned using a 2:1.5:1 ratio respectively (MBRT = 47; SME = 35; NIC = 22). Randomization will occur separately at each site to ensure equal ratios at all sites across the three trial arms. Since we are randomizing at each study site and stratifying for gender, study site and gender will become non-ignorable clusters. Therefore, we will adjust for study site and gender in our statistical models to avoid a deviation in our type I error rate from .05. We will include study site as a covariate in our statistical models. In addition, since including gender and study site as covariates in our statistical models will effectively decrease the sample size even further, we will conduct sensitivity and responsiveness to change analyses with and without covariates to ensure all inferential analyses can be conducted, and will compare the results between models with and without covariates to identify potential Type II Errors in models with covariates included.

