## 5. STUDY INTERVENTIONS

### 5.1 Interventions, Administration, and Duration

Both MBRT and SME will include psychoeducation, gentle movement exercises focused on stress reduction and fitness, and weekly homework assignments, and will be matched for time and assigned homework.

MBRT will be delivered in groups of 10 to 13 law enforcement officers, in 8 weekly sessions of 1 hour each, with the exception of weeks 1 and 7 which are extended 7- and 4-hour classes, respectively, for a total of 17 intervention hours. The extended session, modeled after MBSR, is intended to provide an immersive training experience. The session will contain a series of mindfulness practices, including body scan, mindful movement, and walking and breath-focused

meditations. The session will focus primarily on formal mindfulness practices, in contrast to inclusion of discussion and psychoeducational components contained in other MBRT sessions.

If state, local and university allow Sessions 1 and 7 to be in-person, they will be conducted at the study sites. If not, they will be conducted using the online Zoom platform. Any MBRT in-person intervention sessions will be held in reserved rooms able to accommodate up to 25 people, and large enough to comply with social distancing guidelines - specifically, the Psychology Research Lab in Portland, and at UNM Department of Psychology in Albuquerque. All MPD groups will be conducted remotely. Online groups will be facilitated via Zoom. MPI [name] and Co-Is [name] and [name] will oversee MBRT interventionist training. [name] co-developed MBRT, and is an expert in MBIs with first responders; [name] and [name] have facilitated, trained and supervised MBIs, and have collaborated on multiple MBI-related NIH trials.

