estimates (i.e., Cronbach's alpha), and intraclass correlations will be estimated and checked for discrepancies between sites. Identified discrepancies will be investigated to determine site-specific issues that would undermine assumptions of conceptual and structural equivalence of measurement.

Given the optimization aim of our study, our analyses will not adjust for intraclass correlations across study arms (and any heterogeneity in those correlations). Our study will allow us to obtain information about the magnitude of intraclass correlations and the degree to which they are heterogeneous across study arms, which we will use for our data analysis plan in a future fully-powered efficacy RCT.

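### Site and gender covariates are said to hold type I error at .05, but they do not cover clustering by training group

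*Combined protocol and SAP*

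**What the plan says.** Section 9.2 specifies a one-way comparison of MBRT with SME, and of MBRT with NIC, for each outcome. It then adds study site and gender as covariates. The purpose is introduced with "To adjust for non-ignorable clustering in order", and the resulting F-values are described as unbiased. The section goes on to say that "adjusting for non-ignorable clustering will allow us to avoid deviation from a type I error rate of .05".

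Section 3 makes the same type I error claim but names what it covers: "Since we are randomizing at each study site and stratifying for gender, study site and gender will become non-ignorable clusters".

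Three other places bear on this:

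- Section 3: "The study will use an Individually-Randomized Group Treatment (IRGT) design". The same section describes SME as group-based.
- Section 5.1: "MBRT will be delivered in groups of 10 to 13 law enforcement officers".
- Section 9.6 (Quantitative): "our analyses will not adjust for intraclass correlations across study arms (and any heterogeneity in those correlations"). The ICCs are to be estimated only for the future trial.

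No model in Section 9.2 or 9.6 has a term for training group.

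**The concern.** A type I error rate belongs to the whole test, so it is held only if all the correlation among officers within an arm is dealt with. Fixed terms for site and gender remove differences between sites and between genders. They cannot remove differences between training groups within the same site and arm. If officers taught together end up more alike than officers taught apart, the residual variance understates the uncertainty of the arm contrast, and F is too large on average.

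Section 9.2 therefore gives an assurance that Section 9.6 takes away, and neither refers to the other. Two things are at stake. A designer of the efficacy trial who reads Section 9.2 would take the F-values as protected against clustering. And Section 9.1 names confidence intervals as an aim: an interval for an arm mean or difference computed without regard to training group would be too narrow at a positive ICC.

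**Working it through.** **Inputs from the plan.** Arms 47 / 35 / 22, sites 52 / 26 / 26, ratio 2:1.5:1 (Précis, Section 3). MBRT groups of 10-13 (Section 5.1). NIC has no groups. Attrition: "we predict an overall attrition rate of 20% across our three study arms" (Section 9.2). Nominal level .05.

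**Assumed, because the documents do not say.** Training-group ICC of .02, .05 or .10; SME in four groups (9+8, 9, 9) or three (17, 9, 9); NIC 12/5/5 by site; dropout at random; 16%, 16% and 25% women in Albuquerque, Portland and Madison, as in the Section 3 targets.

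**1. Number and size of MBRT groups.** 47/13 = 3.6 and 47/10 = 4.7, so four is the only whole number of groups that fits. By site, 52 × 2/4.5 = 23.1 and 26 × 2/4.5 = 11.6, giving 12+11, 12 and 12. Mean size m = 47/4 = 11.75, or 0.8 × 47/4 = 9.4 after attrition.

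**2. Variance inflation of the MBRT mean, 1 + (m − 1) × ICC.**

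| ICC | m = 11.75 | m = 9.4 | Interval width ratio, m = 9.4 |
|---|---|---|---|
| .02 | 1.215 | 1.168 | √1.168 = 1.08 |
| .05 | 1.538 | 1.420 | √1.420 = 1.19 |
| .10 | 2.075 | 1.840 | √1.840 = 1.36 |

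**3. Null simulation of the planned model** (least squares on arm, site and gender; 10,000 trials per cell, Monte Carlo SE at most .004; 20% attrition). The first row reproduces the plan's own figure: .05 is obtained when the ICC is zero.

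| ICC | Rejection v SME (4 / 3 SME groups) | Rejection v NIC | Mean F v SME | Mean F v NIC | Coverage, 95% interval for MBRT mean |
|---|---|---|---|---|---|
| 0 | .052 / .048 | .052 | about 1.03 | about 1.03 | about .95 |
| .02 | .066 / .071 | .058 | 1.18-1.22 | 1.11 | .930-.933 |
| .05 | .092 / .101 | .068 | 1.43-1.52 | 1.22 | .900-.908 |
| .10 | .142 / .156 | .088 | 1.87-2.03 | 1.39 | .842-.850 |

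With full retention, rejection v SME is .068/.076, .108/.118 and .157/.188 at the three positive ICCs, and v NIC .056, .073 and .094. The NIC comparison suffers less because only one of its arms is clustered. At a negative ICC of −.02 the error reverses (.037/.032 v SME and .043 v NIC, with attrition).

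**4. Cross-checks.** A separate simulation (20,000 trials per cell, four SME groups, 20% attrition) gave .070, .097 and .146 v SME. The normal approximation 2(1 − Φ(1.96/√VIF)), with both arms in groups of 10 to 13, gives .104-.121 at ICC .05, in line with the full-retention figures. When the eight group means are analysed with site and arm (8 − 4 = 4 error df), rejection is .050, .049, .050 and .050 at ICC 0, .02, .05 and .10. Training group is therefore the missing component.

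**5. Effect on the ranking.** Take two independent outcomes with no true effect and ICCs of .05 and .02. The first has the larger F in 54% of trials v SME and 52% v NIC, where 50% is neutral. With a true effect of d = .3 on both, the figure is 50-51%. The extreme pair, .10 v 0, gives 59-60% v SME and 54% v NIC with no effect, and 52-55% with d = .3.

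**The case against.** Four points can be made for the plan.

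- **Scope.** Section 3 defines the clusters as site and gender, and Section 9.2 names the same two factors when it sets the adjustment. Read with that definition, the sentence is correct. This stands for Section 3. In Section 9.2 the limit is not repeated, and in a trial that calls itself a group treatment design a reader will naturally count training groups among the clusters.
- **Disclosure.** Section 9.6 says openly that ICCs are not adjusted for, and Section 9.2 says no variance inflation factor was used and plans ICC sensitivity for the future trial. This also stands. The omission is deliberate and not hidden. The fault is an unqualified claim that sits beside the disclosure without reference to it.
- **Consequence.** No p-value decides anything, and the F-values only rank outcomes. Step 5 confirms that the ranking hardly moves. This is the strongest point, and it keeps the matter modest.
- **Unspecified intervals.** Section 9.6 specifies no arm intervals, and the only concrete use of intervals in Section 9.2 is for retention rates. That is so. The recommendation on intervals therefore applies only where one is reported, in line with the aim in Section 9.1.

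The sizes do rest on ICCs and SME group sizes that the documents do not give. Section 3 also has the same pair leading MBRT at every site, which may lower the MBRT ICC.

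**Conclusion.** The point holds. The unbiased-F and .05 statements in Section 9.2 are true for the stratification factors and fail for the arm test whenever the training-group ICC is positive. That conclusion follows from the design and does not depend on the simulations.

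The size is conditional on the assumed layout. A modest ICC of .02 moves the error rate only to about .07 against SME, while .10 roughly triples it. Interval coverage is the more practical loss, about five percentage points at ICC .05. The outcome ranking, which is the plan's main use of F, is little affected. This is a statement to correct, with some error bars to qualify. It does not call the design or its main output into question.

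**What to change.** 1. **Limit the sentence in Section 9.2.** For example: *Including site and gender adjusts the F-values and the .05 level for the stratification factors only; they are not adjusted for clustering by training group (see Section 9.6).* Add the same pointer to Section 9.6 in Section 3, whose claim is otherwise correct.
2. **Qualify reported intervals.** Wherever an interval for an arm mean or arm difference is given, print beside it a version with each clustered arm's variance multiplied by 1 + (m − 1) × ICC (factor 1 for NIC), at stated ICCs such as .02, .05 and .10. Label it a sensitivity range, since the true ICC is unknown.
3. **Optional.** Show the ICC estimates already planned beside the F ranking, with a caution that they are imprecise. A partially nested mixed model should also stay optional: with about four groups per arm it is conservative and unstable.

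**Cost.** Wording in two places, and up to three further intervals per reported estimate, which a supplementary table can hold. Training-group membership must be recorded anyway for the planned ICC estimates. At 20% attrition the MBRT-mean interval widens by 8%, 19% or 36% at ICC .02, .05 or .10. The correction is only as good as the ICC chosen: if the true value is .05, coverage is 94-95% using .05, 92-94% using .02 and 96-97% using .10.
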